8.3. Clinically Notable Treatment-Emergent Adverse Events Based on Customized MedDRA Queries

The following categories of clinically notable events will be summarized based on customized MQs (see [Appendix C](#)):

- Anemia
- Neutropenia
- Thrombocytopenia
- QT prolongation
- Hyperlipidemia
- EBV infection
- CMV infection

Within each category, the number and percentage of subjects with at least 1 TEAE occurring during the treatment phase tabulated by MedDRA PT will be summarized. Summaries of clinically notable TEAEs based on customized MQs will be provided by treatment group, category, PT, and the highest grade or outcome.

- Overall summary of clinically notable TEAEs in the treatment phase based on customized MQs
- Number (%) of subjects with clinically notable TEAEs in the treatment phase based on customized MQs by PT and outcome
- Number (%) of subjects with clinically notable TEAEs in the treatment phase based on customized MQs by PT and highest grade

8.4. Clinical Laboratory Tests

Laboratory test values outside the normal range will be assessed for severity based on the normal ranges for the clinical reference laboratory. The incidence of abnormal laboratory values and shift tables relative to baseline will be tabulated.

Laboratory data will be classified into CTC grades for AEs (CTCAE v4.03). The following summaries will be produced for the laboratory data:

- Shift tables using CTC grades to compare baseline with the worst postbaseline value will be produced with CTC grade.
- For laboratory parameters where CTC grades are not defined, shift tables to the worst postbaseline value will be produced using the low/normal/high classifications based on laboratory reference ranges.

Numeric laboratory values will be summarized descriptively in SI units, and non-numeric test values will be tabulated when necessary. In addition, line graphs will be provided for platelets, neutrophils, cholesterol, and triglycerides over time in the treatment phase, plotted by treatment group.

8.5. Vital Signs

Descriptive statistics and mean change from baseline will be summarized for vital signs (blood pressure, pulse, respiratory rate, and body temperature) at each assessment time by treatment group. Vital sign results will be reviewed for clinically notable abnormalities (see [Table 6](#)), and subjects exhibiting clinically notable vital sign abnormalities will be listed. A value will be considered an "alert" value if it is outside the established range and shows a > 25% change from baseline.

Table 6: Criteria for Clinically Notable Vital Sign Abnormalities

Parameter	High Threshold	Low Threshold
Systolic blood pressure	> 155 mmHg	< 85 mmHg
Diastolic blood pressure	> 100 mmHg	< 40 mmHg
Pulse	> 100 bpm	< 45 bpm
Temperature	> 38°C	< 35.5°C
Respiratory rate	> 24 breaths/min	< 8 breaths/min

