### 1.5. Potential Risks and Benefits of the Treatment Regimen

Adverse events that have been most frequently reported in at least 10% of subjects receiving itacitinib monotherapy include anemia, thrombocytopenia, diarrhea, nausea, fatigue, and upper respiratory tract infection.

As a result of itacitinib-mediated immunomodulation, an increased incidence of infections could possibly occur with itacitinib therapy. Strict clinical monitoring is indicated to identify and treat infections in study subjects should they occur.

Because of the potential for myelosuppression, subjects will have hematologic parameters closely monitored during clinical studies. If there are clinically relevant declines in hematology parameters, therapy may be interrupted until resolution or discontinuation. As itacitinib also has the potential to cause WBC margination (ie, a transient decrease in ANC), assessment of hematology parameters should be performed before study drug administration and at all applicable study visits.

As described previously, murine models of JAK/STAT inhibition using both ruxolitinib and itacitinib have demonstrated a decrease in the expression of CXCR3, reduction of GVHD, preservation of the beneficial GVT effect, and improvement in survival. [REDACTED]

[REDACTED]

In INCB 39110-108, treatment interruptions and stepwise 100 mg dose reductions were used to manage toxicity. In an analysis of the data, efficacy was not affected in subjects who demonstrated Day 28 response and had a dose reduction for any reason. Dose reductions also facilitated platelet recovery in subjects with platelet count decreases receiving treatment, although recovery was also observed in subjects who did not have a dose reduction. Thus, the proposed tapering schedule is not expected to negatively impact efficacy in responding subjects, and clinicians are permitted to re-escalate the dose of itacitinib or placebo in subjects who initiate a taper but subsequently begin to demonstrate signs or symptoms of GVHD progression.

[REDACTED]

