### **3.2. Subject Exclusion Criteria**

1. Has received more than 1 allo-HSCT.
2. Has received more than 2 days of systemic corticosteroids for acute-GVHD.
3. Presence of GVHD overlap syndrome.
4. Presence of an active uncontrolled infection. An active uncontrolled infection is defined as hemodynamic instability attributable to sepsis or new symptoms, worsening physical signs, or radiographic findings attributable to infection. Persisting fever without signs or symptoms will not be interpreted as an active uncontrolled infection.
5. Known human immunodeficiency virus infection.
6. Active HBV or HCV infection that requires treatment, or at risk for HBV reactivation (ie, positive HBsAg). Subjects with negative HbsAg and positive total HB core antibody may be included if HBV DNA is undetectable at the time of screening. Subjects who are positive for HCV antibody are eligible only if polymerase chain reaction test is negative for HCV RNA. Subjects whose immune status is unknown or uncertain must have results confirming immune status before enrollment. Prior serology results are acceptable for determining eligibility.
7. Subjects with evidence of relapsed primary disease, or subjects who have been treated for relapse after the allo-HSCT was performed.
8. Any corticosteroid therapy for indications other than GVHD at doses > 1 mg/kg per day methylprednisolone (or prednisone equivalent) within 7 days of randomization.
9. Severe organ dysfunction unrelated to underlying GVHD, including:
  - a. Cholestatic disorders or unresolved veno-occlusive disease of the liver (defined as persistent bilirubin abnormalities not attributable to GVHD and ongoing organ dysfunction).
  - b. Clinically significant or uncontrolled cardiac disease, including unstable angina, acute myocardial infarction within 6 months of enrollment, New York Heart Association Class III or IV congestive heart failure, circulatory collapse requiring vasopressor or inotropic support, or arrhythmia that requires therapy.
  - c. Clinically significant respiratory disease that requires mechanical ventilation support or 50% oxygen.
10. Serum creatinine > 2.0 mg/dL or creatinine clearance < 40 mL/min measured or calculated by Cockcroft-Gault equation.
11. Currently breast feeding.

12. Receipt of live (including attenuated) vaccines or anticipation of need for such a vaccine during the study.

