4.1.3. Baseline Value

Baseline is the last nonmissing measurement obtained before or on the first day of itacitinib or placebo administration (in terms of date and time, if available).

4.1.4. Retreatment Day 1

Retreatment Day 1 is the date of first dose of itacitinib in the retreatment phase.

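### The > 25% change condition makes the vital-sign alert label inoperative for body temperature; only the label is affected

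*SAP*

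**What the plan says.** SAP 8.5 plans descriptive statistics and mean change from baseline for "vital signs (blood pressure, pulse, respiratory rate, and body temperature) at each assessment time by treatment group". Table 6 of the SAP gives a high and a low threshold for systolic and diastolic pressure, pulse, temperature and respiratory rate. The temperature row is > 38°C and < 35.5°C. The section then makes two separate provisions:

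- Listing: "subjects exhibiting clinically notable vital sign abnormalities will be listed". This sentence points to Table 6 and carries no change-from-baseline condition.
- Alert label: a value is an alert if it is "outside the established range and shows a > 25% change from baseline". The two conditions are joined by *and*, and no parameter is exempted.

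Protocol 9.4.4.3 has the same alert rule, and Protocol Table 9 has the same thresholds. SAP 4.1.3 defines the comparator: "Baseline is the last nonmissing measurement obtained before or on the first day of itacitinib or placebo administration". Neither document gives temperature a change criterion of its own.

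**The concern.** A 25% relative change is a workable filter for blood pressure, pulse and respiratory rate, whose values vary widely in relation to their mean. Body temperature does not: the whole interval between the two Table 6 limits is 2.5°C on a level of about 37°C. A percentage of a Celsius value also has no natural meaning, since the zero of the scale is arbitrary. If no realistic temperature can meet both conditions, the plan contains a prespecified safety classification that cannot be triggered for one of its parameters. What is at stake is whether that label says anything about temperature in a trial where Protocol 1.5 warns that "an increased incidence of infections could possibly occur with itacitinib therapy".

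**Working it through.** The documents give no figure to reproduce here, so the check is direct arithmetic on the rule.

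**Inputs.** Temperature limits of 38°C and 35.5°C (SAP Table 6, Protocol Table 9); change condition > 25% (SAP 8.5, Protocol 9.4.4.3); baseline *B* as in SAP 4.1.3. The values of *B* are assumptions, because the documents give no distribution of baseline temperature.

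**Formulas.** A high alert needs T > max(38, 1.25 × *B*). A low alert needs T < min(35.5, 0.75 × *B*).

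| Baseline *B* (°C) | High alert needs T above | Low alert needs T below |
|---|---|---|
| 33 | 41.25 | 24.75 |
| 35.5 | 44.4 | 26.6 |
| 36 | 45.0 | 27.0 |
| 37 | 46.25 | 27.75 |
| 38 | 47.5 | 28.5 |
| 39 | 48.75 | 29.25 |
| 40 | 50.0 | 30.0 |

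In every row the 25% condition decides the result and the Table 6 limit plays no part.

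**Size of realistic changes.**
- From one Table 6 limit to the other: 38/35.5 − 1 = +7.0%; 35.5/38 − 1 = −6.6%.
- From 37°C to 42°C: 42/37 − 1 = +13.5%. From 37°C to 30°C: 30/37 − 1 = −18.9%.
- For 38°C itself to be a 25% rise, baseline would have to be 38/1.25 = 30.4°C. For 35.5°C to be a 25% fall, baseline would have to be 35.5/0.75 = 47.3°C.

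**Febrile baseline.** Subjects may enter with fever, since Protocol 3.2 says: "Persisting fever without signs or symptoms will not be interpreted as an active uncontrolled infection". That moves the high threshold further away: from 39°C, an alert needs more than 48.75°C.

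**Fahrenheit.** From 98.6°F, 1.25 × 98.6 = 123.25°F (50.7°C) and 0.75 × 98.6 = 73.95°F (23.3°C). The same rule gives different thresholds on the two scales, and the Fahrenheit ones are stricter.

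**Other parameters, at assumed ordinary baselines.**

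| Parameter | Baseline | Change at high limit | Change at low limit |
|---|---|---|---|
| Systolic pressure | 120 | 155/120: +29% | 85/120: −29% |
| Diastolic pressure | 75 | 100/75: +33% | 40/75: −47% |
| Pulse | 75 | 100/75: +33% | 45/75: −40% |
| Respiratory rate | 16 | 24/16: +50% | 8/16: −50% |

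For these four, crossing the Table 6 limit already exceeds 25%, so the rule works. The 25% condition mainly screens out subjects who start near a limit. Only temperature is disabled.

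**The case against.** The best case against raising this is that nothing of substance depends on the label. That largely stands.

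A reader might infer that the rule hides a difference in fever between arms, or that the report will show a misleading count of zero temperature alerts. The documents do not support either reading:

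- Temperature is summarised by treatment group at each assessment (SAP 8.5; Table 3.4.5 in SAP Appendix B).
- Subjects with values beyond Table 6 are listed without any 25% condition, and Appendix B plans Listings 2.9.1 and 2.9.2 for abnormal and for all vital-sign values.
- Abnormalities that the investigator judges clinically significant are reported as adverse events (Protocol 7.5.3). Treatment-emergent events are tabulated by arm (SAP 8.2.2), and EBV and CMV infections have their own customised queries (SAP 8.3).
- No table that counts alerts is planned. Part of Appendix B is missing from the text available, but its block on laboratory values, vital signs and ECGs is present and names no alert output. Neither document ties an action to the label. The contents of the DMC charter cannot be seen.

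A reader might also take infection to be the one risk the protocol names. Protocol 1.5 names myelosuppression as well, and it relies on clinical monitoring to detect infection, not on this label.

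What the objection does not remove is the error itself: the rule covers temperature as written, and no realistic temperature satisfies it.

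**Conclusion.** The point holds as a drafting error of minor severity. For baselines across the Table 6 range, a temperature alert would need a reading above 44.4 to 47.5°C or below 26.6 to 28.5°C, so the category will be empty whatever the true frequency of fever or hypothermia. The alert label then carries no information on temperature, and an absence of temperature alerts must not be read as an absence of fever.

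The one outside assumption is the plausible range of body temperature, and the result is not sensitive to it. Only an extreme baseline, near 33°C or at 40°C and above, brings either threshold close to 41°C or 30°C. Efficacy, type I error, sample size and the planned by-arm safety tables are unaffected.

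**What to change.** In SAP 8.5 and Protocol 9.4.4.3, limit the 25% condition to blood pressure, pulse and respiratory rate. For temperature, class a value as an alert on the existing Table 6 thresholds alone, or on those thresholds plus an absolute change in degrees that the sponsor fixes before unblinding.

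With the thresholds alone, alert and clinically notable become the same thing for temperature. If the sponsor wants the alert to be a stricter class, the absolute change is the option to take.

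The cost is one sentence in each document and a small programming change. No new data are needed. More temperature values will be classed as alerts, which is the purpose.

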8.6. Electrocardiograms

Electrocardiogram results will be reviewed for clinically notable abnormalities according to predefined criteria (see [Table 7](#)). Subjects exhibiting clinically notable ECG abnormalities will be listed and summarized by treatment group. Adverse events will be reported for clinically notable abnormalities that are considered clinically significant in the judgment of the investigator.

Descriptive statistics (N, mean [SD], minimum, median, and maximum) at baseline for each parameter will be summarized by treatment group. At EOT, summary statistics of mean change (SD) and percentage change will also be tabulated by parameter and treatment group.

Table 7: Criteria for Clinically Notable ECG Abnormalities

Parameter	High Threshold	Low Threshold
QTcF	> 460 ms	< 295 ms
PR	> 220 ms	< 75 ms
QRS	> 120 ms	< 50 ms
QT	> 500 ms	< 300 ms
RR	> 1330 ms	< 600 ms

QTcF = Fridericia correction.

9. INTERIM ANALYSES AND FINAL ANALYSES

9.1. Overview of Interim Analyses

There are 2 planned interim analyses. The first interim analysis is for futility checking and second interim analysis is for efficacy and futility.

9.1.1. Interim Analysis 1

The first interim analysis for futility only will be performed when 112 (25.7% of the planned 436 subjects) have completed the Day 28 visit or withdrew early from study. No alpha will be spent during the first interim analysis. The stopping rule is nonbinding. When the conditional power is < 20%, the sponsor may consider terminating the trial if the totality of evidence is warranted.

Interim Analysis 1 on ORR at Day 28 will be carried out as follows:

F1: Obtain CMH test statistic (chi-square test with degree of freedom 1);

F2: Obtain observed normalized test statistic z by taking square root of CMH in F1;

F3: Calculate conditional power based on $\Phi\left(\frac{z}{\sqrt{t(1-t)}} - \frac{z_{\alpha/2}}{\sqrt{1-t}}\right)$ (Jennison and Turnbull 1999),

where Φ is the cumulative distribution function of the observed normalized test statistic z . t is the information fraction and (ie, observed sample at interim divided by planned total sample size 436); $t = 0.257$ at Interim 1 and $z_{\alpha/2} = 1.96$.

F4: If conditional power is less than 20%, the sponsor may consider stopping the study for futility; otherwise, the study will continue.

9.1.2. Interim Analysis 2

For Interim Analysis 2, the analysis of both efficacy and futility will use a clinical database cutoff based on when 240 eligible subjects (55.0% of the targeted 436 subjects) have completed the Day 180 visit or withdrawn from the study prior to Day 180.

The Hwang-Shih-DeCani alpha spending function with shape parameter -4 (O'Brien Fleming like boundary) will be used to define nonbinding upper efficacy boundary for the primary analysis of ORR at Day 28 when approximately 240 eligible subjects reach Day 180. Based on enrollment projection, there will be approximately 360 subjects who have completed Day 28.

The futility analysis based on test of ORR at Day 28 at Interim Analysis 2 will be carried out the same way as in Interim Analysis 1 (Steps F1-F4) but using the observed information fraction and observed normalized test statistic from Interim Analysis 2.

[Table 2](#) lists efficacy boundary when information fraction (ie, the percentage of subjects) is 0.826 (360 subjects complete Day 28 or withdraw from the study) at Interim Analysis 2. If the test on ORR at Day 28 crosses the boundary, then the key secondary endpoint, 6-month NRM rate, will be tested using a separate boundary using the Bonferroni method for alpha-spending (ie, 0.0125 as compared with 1-sided p-value at both interim and final analyses). Note that [Table 2](#) will be re-derived when the observed information for ORR at Day 28 is not 0.826.

Therefore, efficacy analysis at Interim 2, assuming information fraction being 0.826 (ie, 360/436) will be conducted as follows:

- E1: Obtain CMH test statistic on ORR at Day 28 (chi-square test with degree of freedom 1),
- E2: CMH test statistic will be compared with the critical value in Column 7 of [Table 2](#) (Interim 2 chi-square test critical value),
- E3: If positive on ORR at Day 28, NRM rate at Day 180 will be tested using the Bonferroni method,
- E4: If neither efficacy nor futility on Day 28 ORR is crossed, study will continue.

Assuming that at the Interim Analysis 2 data cutoff date (Day 180 of the 240th randomized eligible subject) there are approximately 360 subjects based on estimation who have been randomized, then testing of Day 28 ORR will be conducted for subjects who have completed Day 28 or withdrawn from the study upon the cutoff date. This means that, by the Interim Analysis 2 data cutoff date, subjects who were ongoing but had not reached the Day 28 visit will be excluded for both the Day 28 ORR and Day 180 NRM analyses.

Analysis of NRM rate at Day 180 will use the same method as described in Section [7.4.1](#) for final analysis but using the Interim Analysis 2 cutoff data instead. The decision process is described in [Figure 4](#).

At the Interim Analysis 2 data cutoff date, if the total number of randomized subjects in the Interim 2 analysis set is different from the predicted number 360, the efficacy boundaries will be recalculated based on the actual observed information fraction at Interim Analysis 2.

An independent DMC will be charged with evaluating interim results. The DMC will consist of clinicians and an independent statistician. The sponsor will remain blinded, and DMC decisions will be communicated through sponsor management as dictated in the DMC charter. Additional operational details of the interim analyses, including tables, figures, and listings provided to the DMC, will be provided in the DMC Charter.

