The first interim analysis for futility only will be performed when 112 subjects (25.7% of the planned 436 subjects) have completed the Day 28 visit or withdrew early from study. No alpha will be spent during the first interim analysis. The stopping rule is nonbinding. When the conditional power is < 20%, the sponsor may consider terminating the study if the totality of evidence is warranted. The conditional power is calculated assuming that the estimated treatment effect at the interim analysis is the true effect using the formula (Jennison and Turnbull 1999):

$$\Phi \left(\frac{z}{\sqrt{t(1-t)}} - \frac{z_{\alpha/2}}{\sqrt{1-t}} \right)$$

where Φ is the cumulative distribution function of the observed normalized test statistic z , and t is the information fraction (ie, observed sample at interim divided by the planned total sample size 436); $t = 0.257$ at Interim 1 and $z_{\alpha/2} = 1.96$.

Since CMH test with only 1 stratification factor, aGVHD risk status (standard vs high risk), will be used to test ORR at Day 28, it is thus a chi-square test with degree of freedom equal to 1, that is, $\chi^2_{df=1}$. Taking the square root of the observed CMH test statistic $\chi^2_{df=1}$ will result in normalized test statistic z .

3.4.2. Interim Analysis 2

For Interim Analysis 2, the analysis of both efficacy and futility will use a clinical database cutoff based on when 240 eligible subjects (55.0% of the targeted 436 subjects) have completed the Day 180 visit or withdrew from the study prior to Day 180.

The Hwang-Shih-DeCani alpha spending function with shape parameter -4 (O'Brian-Fleming like boundary) will be used to define upper efficacy boundary for the primary analysis of ORR at Day 28 when approximately 240 eligible subjects reach Day 180 (Hwang et al 1990). Based on enrollment projection, there will be approximately 360 subjects who have completed Day 28.

Table 2 lists efficacy boundary when information fraction (ie, the percentage of subjects) is 0.826 (360 subjects complete Day 28) at Interim 2; if ORR tested at Day 28 crosses the boundary, then the key secondary endpoint, 6-month NRM rate, will be tested by using the Bonferroni method for alpha spending (ie, 0.0125 as compared with 1-sided p-value at both interim and final analyses). By simulation, without considering early stopping for futility, the power of testing 6-month NRM at Interim 2 (with 240 eligible subjects who have completed Day 180) is approximately 0.608.

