7.2. Efficacy Hypotheses

The primary efficacy analysis is the comparison of ORR at Day 28 between the 2 treatment groups. The following statistical hypotheses will be tested to address the primary efficacy objective:

$$H_0: ORR_{itacitinib} = ORR_{pbo} \text{ versus } H_1: ORR_{itacitinib} > ORR_{pbo}$$

where $ORR_{itacitinib}$ and ORR_{pbo} are the ORRs at Day 28 in the itacitinib and placebo groups, respectively. The CMH chi-square test, stratified by the randomization stratification factor (ie, standard risk and high risk), will be used to compare ORR between the 2 treatment groups, at the 1-sided 2.5% level of significance.

For the primary efficacy analyses, Day 28 ORR, as well as ORR for scheduled visits at Days 14, 56, 100, and 180, if available, will be used; if a scheduled assessment is not available but an unscheduled visit is available (within 3 days of the scheduled date), then the unscheduled assessment closest to the scheduled date will be used.

For summary analyses over time, analysis visits are defined Section 4.1.5, where analysis visits will be used in both tables and figures. The listings will include all collected data from the eCRF regardless of whether the visits are scheduled or unscheduled.

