APPENDIX A. STATISTICAL MODELS FOR EFFICACY ANALYSES

Analysis for Overall Response

Cochran-Mantel-Haenszel test

The null hypothesis of equality of response rate in the 2 treatment groups will be tested against 1-sided alternative. The statistical hypotheses are:

$$H_0: \text{ORR}_{\text{trt}} \leq \text{ORR}_{\text{pbo}} \text{ versus } H_1: \text{ORR}_{\text{trt}} > \text{ORR}_{\text{pbo}}$$

where ORR_{trt} is the probability of response in treatment group and ORR_{pbo} is the probability of response in placebo group. The CMH chi-square test X2CMH (implemented again via SAS procedure FREQ with CMH option in the TABLES statement) will be used to test the difference in response rates between the treatment groups. The p-value corresponding to the CMH test for “general association” will be used, which follows a Chi-square distribution with 1 degree of freedom.

If the sampling assumptions for chi-square test is not met, the exact CMH test will be used (implemented via SAS procedure MULTTEST). The test is performed by running a stratified version of the Cochran-Armitage permutation test (Armitage et al 1969). In studies with stratified randomization, the chi-square approximation is considered appropriate for the X2CMH statistics if the rule of Mantel and Fleiss (1980) is satisfied.

Logistic Regression

Odds ratio will be used as a measure of association between treatment and response. The odds ratio will be derived from the logistic regression model (implemented using SAS procedure LOGISTIC, with both treatment and stratification factor specified as an explanatory variable in the CLASS statement), which allows for including not only the stratification factor but also for adjustments for other covariates (both categorical and continuous). The odds ratio will be presented with 95% Wald confidence limits.

In cases where an exact test has been used to compare response rates, the odds ratio should be determined using exact logistic regression, and the odds ratio presented with exact 95% confidence limits. In these cases, SAS PROC LOGISTIC with EXACTONLY option will be used.

Analyses for Survival Data

Analyses for Survival Data in this section use OS as an example.

Stratified Log-Rank Test

The null hypothesis stating that OS distributions of the 2 treatment groups are equivalent will be tested against 1-sided alternative

Assuming proportional hazards for OS, the following statistical hypotheses will be tested:

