$$H_{02}: \theta_2 \geq 1 \text{ versus } H_{A2}: \theta_2 < 1$$

where θ_2 is the OS hazard ratio (treatment versus placebo). The analysis to test these hypotheses will consist of a stratified log-rank test at an overall 1-sided 2.5% level of significance. The stratification will be based on the randomization stratification factors (ie, aGVHD high vs standard).

The stratified log-rank test adjusting for the strata used in the randomization will be implemented as follows: In each of the K strata separately, the LIFETEST procedure with **STRATA** statement including only the treatment group variable and with the TIME statement will be used to obtain the rank statistic S_k and variance $\text{var}(S_k)$ where $k=1, 2, \dots, K$. The final test statistics will then be reconstructed as follows:

$Z = [S_1 + \dots + S_K] / \sqrt{[\text{var}(S_1) + \dots + \text{var}(S_k)]}$. One-sided P-value will be obtained from the standard normal distribution using the Z statistic.

(One-sided will be obtained using Z statistic / Two-sided p-value will be obtained using Z^2 statistic.)

Kaplan-Meier Estimates

An estimate of the OS survival function in each treatment group at distinct event times will be constructed using KM (product-limit) method as implemented in PROC LIFETEST with METHOD=KM option. The PROC LIFETEST statement will use the option CONFTYPE=LOGLOG. Stratification factor (high vs standard) will be use in **STRATA** statement to get KM estimates by both treatment group and stratum.

Median survival for each treatment group will be obtained along with 95% CIs calculated from PROC LIFETEST output using the method of ([Brookmeyer and Crowley 1982](#)). Kaplan-Meier estimates of the survival function with 95% CIs at specific time points will be summarized. The standard error of the KM estimate will be calculated using Greenwood's formula ([Collett 1994](#)).

Hazard Ratio

Hazard ratio will be estimated by fitting the Cox proportional hazards model using SAS procedure PHREG.

A stratified unadjusted Cox model will be, that is, the MODEL statement will include the treatment group variable as the only covariate and the **STRATA** statement will include stratification variable(s).

Hazard ratio with 2-sided 95% CI will be based on Wald test.

The above survival analyses (ie, log-rank test, KM method and Cox proportional hazards model) do not consider competing risk to be an issue.

Table No.	Title	Population	Standard	In-Text

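### The futility z is an unsigned square root of the CMH chi-square, so a result favouring placebo can read as at least 20% conditional power and 'continue'

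*SAP*

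**What the plan says.** SAP Section 3.4.1 obtains z by "Taking the square root of the observed CMH test statistic", a chi-square with 1 degree of freedom. Step F2 in Section 9.1.1 repeats the instruction: "Obtain observed normalized test statistic z by taking square root of CMH in F1". Step F3 puts this z into the conditional power formula. Step F4 lets the study continue unless conditional power is below 20%. Section 9.1.2 reuses F1 to F4 at Interim 2 with that look's information fraction and z.

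Other parts of the SAP are directional:

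- Section 3.4.1 calculates conditional power "assuming that the estimated treatment effect at the interim analysis is the true effect".
- Section 7.2 states that the CMH test "will be used to compare ORR between the 2 treatment groups, at the 1-sided 2.5% level of significance", with the alternative that itacitinib has the higher response rate.
- Appendix A says of the CMH test: "The null hypothesis of equality of response rate in the 2 treatment groups will be tested against 1-sided alternative". The statistic it then names is one "which follows a Chi-square distribution with 1 degree of freedom", which carries no direction.
- For the log-rank test, Appendix A does spell out a directional statistic: "One-sided P-value will be obtained from the standard normal distribution using the Z statistic". The CMH steps have no equivalent.

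Protocol Section 9.2.1 gives the same conditional power formula with an observed normalized z and no square-root step.

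**The concern.** Conditional power under the current trend depends on which way the trend points. With an unsigned root, the formula receives the size of the interim difference but not its direction. A result that clearly favours placebo is then scored as if it favoured itacitinib by the same amount. The larger the harm, the higher the reported conditional power, so the futility flag becomes less likely as the drug does worse.

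F1 to F4 is the recipe an independent programmer would implement, and standard CMH output is an unsigned chi-square. A DMC could therefore be handed a reassuring conditional power when the SAP's own definition gives essentially zero.

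**Working it through.** **Inputs.** Information fractions are t = 112/436 = 0.257 (Interim 1) and t = 360/436 = 0.826 (Interim 2, the SAP's illustrative case). The critical value in the formula is 1.96. Placebo response rates are 68% (standard risk) and 44% (high risk), mixed 50:50 (SAP Section 3.3). The formula is CP = Φ( z/√(t(1−t)) − 1.96/√(1−t) ).

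**The plan's own figures.** Setting CP = 0.20 gives z = √(t(1−t)) × (Φ⁻¹(0.20) + 1.96/√(1−t)). The result is 0.6257 at Interim 1 and 1.4617 at Interim 2, matching the SAP's 0.626 and 1.46.

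**Interim 1 example (illustrative counts).** Itacitinib 16/28 standard risk and 9/28 high risk (25/56); placebo 19/28 and 12/28 (31/56).

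- Observed minus expected responders on itacitinib: −1.5 in each stratum, sum −3.0.
- Variance: 28 × 28 × 35 × 21 / (56² × 55) = 3.341 in each stratum, sum 6.682.
- CMH chi-square = 9/6.682 = 1.347, so |z| = 1.161.
- As written: 1.161/0.4369 − 1.96/0.8620 = 2.656 − 2.274 = 0.383, so CP = 64.9% and the rule says continue.
- Signed: −2.656 − 2.274 = −4.930, so CP = 4 × 10⁻⁷ and the rule flags futility.
- Swapping the arms also gives 64.9%: the written step cannot tell the two results apart.

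**Interim 2 example (illustrative counts, 90 per stratum per arm).** Itacitinib 53/90 and 32/90 (85/180); placebo 61/90 and 40/90 (101/180).

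- Sum of observed minus expected −8.0, variance 21.369, chi-square 64/21.369 = 2.995, |z| = 1.731.
- As written: 1.731/0.3794 − 1.96/0.4175 = 4.562 − 4.695 = −0.133, so CP = 44.7%.
- Signed: −4.562 − 4.695 = −9.256, so CP = 1 × 10⁻²⁰.

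**Where the flag is lost.** By normal approximation, an observed deficit of about 5.8 points at Interim 1 or 7.5 points at Interim 2 is enough. In whole counts at these rates, the first deficits that lose the flag are 4/56 (7.1 points) and 14/180 (7.8 points).

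**How often.** With no true effect, the normal approximation gives a flag probability of Φ(b) signed and Φ(b) − Φ(−b) as written, where b is the boundary: 73.4% against 46.8% at Interim 1, and 92.8% against 85.6% at Interim 2. A stratified CMH simulation (400,000 runs; 28 or 90 per stratum per arm; the same deficit in both strata) gives:

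| True effect | Interim 1: signed / as written | Interim 2: signed / as written |
|---|---|---|
| None | 75% / 50% | 93% / 86% |
| 5 points worse (assumed) | 89% / 44% | 99% / 68% |
| 10 points worse (assumed) | 96% / 30% | over 99.9% / 31% |
| Design alternative (81%/61% vs 68%/44%) | 15.0% / 14.1% | 5.6% / 5.6% |

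The no-effect simulation differs from the normal approximation at Interim 1 because counts are discrete.

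**Type I error.** Counting only crossings that favour itacitinib, the probability of exceeding 2.2498 at Interim 2 or 2.0155 at the final analysis, with correlation √(360/436), is 0.0250 under the null.

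**The case against.** The strongest reply is that nobody would run it this way. The hypotheses are one-sided. SAP Figure 3 is titled as showing a lower futility boundary, and the stopping rule acts when z falls below it. The protocol's formula has no square root, and Section 7.3.1.1 has the response difference and odds ratio reported beside the CMH p-value. The rule is nonbinding, and an independent DMC evaluates the results. The DMC charter and Figures 3 and 4, which cannot be seen here, may state the direction. The Interim 1 cutoff (25 JUN 2018) also precedes this SAP version (23 JUL 2019). Section 10.2.1 says the conditional power formula in Section 9.1 was corrected in this amendment, so the wording in force at Interim 1 is unknown.

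Much of this stands. The intent can be inferred, the practical consequence is limited, and nothing in the documents shows that any look was programmed unsigned. It does not repair the step, though. The comparisons with 0.626 and 1.46 use the same z that Section 3.4.1 has just defined as an unsigned root, so a lower boundary does not give it a sign. A charter may help, but the SAP's own procedure should give the answer its own definition requires.

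It is also fair to say that step E2 (Sections 9.1.2 and 9.2) compares an undirected chi-square with its critical value and can be read sensibly, because E3 asks for a positive result and Section 3.4.2 speaks of an upper boundary. That makes E2 a matter for clarification only.

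**Conclusion.** The point holds. As written, z cannot be negative, and the futility rule gives the wrong answer for a result that favours placebo by more than the boundary. This is an error in a written step, not a different intended analysis.

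If the step is followed literally, conditional power is reported as 65% or 45% in the two worked examples, where the SAP's definition gives under 0.001%. Under a true deficit of 5 points, the flag rate falls by about 45 percentage points at Interim 1 (89 − 44) and 31 at Interim 2 (99 − 68). These figures rest on the SAP's control rates, equal strata, the illustrative 360 subjects at Interim 2, and deficits that are assumed. Type I error is unaffected, provided an efficacy crossing counts only when it favours itacitinib.

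**What to change.** - In Section 3.4.1 and step F2, define z as the square root of the CMH statistic carrying the sign of the stratified response rate difference, itacitinib minus placebo.
- In step E2 of Sections 9.1.2 and 9.2, state that the boundary is crossed only when the difference favours itacitinib.
- Both interim cutoffs (25 JUN 2018 and 17 APR 2019) precede this SAP version. Have the independent statistician confirm that z was signed at Interim 1 and, if it has been run, at Interim 2.

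The cost is one phrase in each of four places and one confirmation. The 20% threshold, the 1.96, all boundaries, alpha and sample size stay as they are. Under the design alternative, signing z raises the futility flag rate from 14.1% to 15.0% at Interim 1 and leaves it at 5.6% at Interim 2.
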